only control algorithms of which we are aware, the adaptive basal insulin algorithm obviates the need for the user to set, or even know, his or her "basal-rate profile". Instead, it is capable of automatically adapting to, and compensating for, changes in an individual's basal insulin need, such as might occur over a period of hours, days, or weeks (e.g. circadian hormonal fluctuations, intercurrent illness, physical activity, or emotional state) or as might occur over a period of months or years due to developmental changes (e.g. hormonal changes that occur during puberty or menopause). Our adaptive meal dose controller obviates the need for the user to set, or even know, his or her "carbohydrate-to-insulin ratios", as it makes automatic adjustments based on dosing history for similar meal announcements made on previous days, and customizes the dose for each individual and for time of day.

Taken together, these mathematical algorithms provide a universal framework for a glycemic control strategy that requires no quantitative input from, or participation by, the user (besides entering body weight to initialize the system), but which automatically adapts insulin dosing to meet the individual needs of each user. Another challenge we have met is enabling the technology to remain completely autonomous in managing insulin delivery even when the Dexcom CGM is offline. Specifically, when the Dexcom CGM is offline, the BP invokes the high-resolution "basal rate profile" that it had recently learned and stored when the Dexcom CGM was online. On the basis of what the system learned and stored about meal announcements when the Dexcom CGM was online, it is able to respond to meal announcements in the same manner when the Dexcom CGM is offline. Finally, it automatically responds to user-entered BG values when the Dexcom CGM is offline by issuing a correction dose of insulin or glucagon based on what it learned about the user's insulin and glucagon needs when the Dexcom CGM was online. Thus, the BP never relies on, or burdens the user with, the determination of subjective dosing decisions, which inevitably vary in quality and reliability among different users. The BP provides a turnkey solution for people with diabetes that comprehensively manages glycemia across a broad range of individual needs and across a large spectrum of circumstances and challenges to glycemic control.

I.c. Preliminary Studies

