Infusion sets: Subjects will wear one FDA approved commercially available leur-lock compatible infusion set throughout the duration of the study. If an infusion set falls off or is clinically suspected of failing, it will be replaced with a new one. The infusion set will be changed at least every 48 hours.

Continuous glucose monitor (CGM) Sensor: One transcutaneous glucose sensor for the Dexcom G5 CGM will be inserted in the SC tissue and will provide input to the controller. The sensor is powered by the battery within the transmitter that clips to the sensor. The whole assembly is held to the skin with an adhesive patch and communicates wirelessly via Bluetooth Low Energy with the Dexcom G5 application running on the iPhone 6S. If the G5 sensor fails for any reason during the experiment it will be replaced promptly. The G5 sensor will be replaced at least every 7 days.

iPhone 6s: The Dexcom G5 app is installed and run on a stock iPhone 6s running iOS 12. The Dexcom G5 app captures CGM glucose values and transmits the data via Bluetooth Low Energy to the bionic pancreas control algorithm running on the iLet.

iLet Bionic Pancreas: The iLet bionic pancreas has an integrated graphical user interface (GUI) and touchscreen display that displays the current CGM glucose, a graphical history of the CGM glucose, and doses of insulin delivered by the control algorithm. The GUI can also be used to input optional meal announcements, designating the size of the meal as "Large for Me" "Typical for Me", "Small for Me", or "Tiny for Me", and the mealtime as the "Start", "Middle", "End", or "Sleeping" periods of the day. This will trigger a partial meal-priming bolus, the

size of which will adapt during the course of the trial to meet a target of 75% of the insulin needs for that size and mealtime.

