- A urine pregnancy test will be performed in female volunteers at the start of the first arm. If the test is positive the volunteer will be informed of the result and the visit will be ended. The date of the last menstrual period will also be documented.
- Study staff will review any changes in the participant's medical history or medications to ensure continued eligibility, and any adverse events that may have occurred since their screening visit.
- The subjects will place a Dexcom G5 sensor and study staff will confirm they are doing it properly.
- Study staff will provide supplies and review the study procedures. The insulin the subject has been assigned to for that week will be provided. Study staff will supervise the setup of the iLet and infusion set.
- The control algorithm will be initialized only with the subject's weight. Diagnostics will be performed to ensure that the Dexcom CGM device is appropriately calibrated and that all the components of the bionic pancreas are in good communication with each other.
- The subject's own insulin infusion pump will be stopped and disconnected, and its infusion set will be removed.

removed.

- Study staff will start the bionic pancreas and will verify that data streaming is working prior to the subject leaving the Diabetes Research Center.

Days 1-7:

- The subjects will calibrate the Dexcom CGM twice daily, preferably before breakfast and supper, using the Contour Next One.
 - Subjects will be advised to delay calibration if there is a steep rise or fall in the blood glucose (>2 mg/dl/min) or if there has been carbohydrate intake in the last 30 minutes. In the immediate aftermath of carbohydrate intake, it is possible for the BG to be rising without a change in interstitial fluid glucose. If a calibration is delayed for any of these reasons, it will be performed at the next opportunity.

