 - If the BG measurement is not consistent with the CGM: the subject will calibrate the Dexcom CGM as long as there has been no carbohydrate intake in the last 30 minutes and there is no steep rise or fall in glucose (>2 mg/dl/min). If a calibration is delayed for this reason, it will be performed at the next opportunity.
 - If the BG measurement is consistent with the CGM: the subject will investigate their insulin infusion site and consider replacing it, check for any occlusions along the insulin fluid path, and check to make sure that the insulin cartridge is not empty.
 - Subjects will be asked and strongly encouraged to announce the three major meals of the day, but not snacks, to the bionic pancreas. The meal announcement will consist of choosing the type of meal (breakfast, lunch, dinner) and the size of the meal relative to typical meals for that subject (tiny, small, typical, large).

Meal Challenges

- During all study arms, subjects will be asked to complete two meal challenges at home to help identify any changes in glucose control on each insulin in response to a standardized meal and bolus.
- Meal challenges will be completed twice in each arm, and must be done during days 3-7, but not on the first 2 days of the arm.
- All meal challenges will be completed using a BOOST High Protein 8-ounce meal replacement drink. This will be provided to the subject at the beginning of each arm.
- Subjects will be asked to follow the protocol below:
 - Fast after 10:00 PM. Only water and non-caloric beverages will be allowed. Subjects will be instructed to follow the same protocols for any hypoglycemia or hyperglycemia that occurs during the fasting period. They will be asked to limit hypoglycemia treatment to simple, rapid-acting carbohydrates over complex carbohydrates wherever possible. Subjects will be encouraged to have a bedtime snack prior to initiating fasting as needed. They will be encouraged to contact study staff with any questions, and remote monitoring will remain in place.
 - Announce no meals on the BP after 10:00 PM.
 - After at least approximately 8 hours of fasting, all subjects will be required to check a fingerstick glucose immediately prior to beginning the meal challenge and use that glucose to calibrate their Dexcom G5 CGM.

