 - Subjects will be instructed to announce the BOOST drink to the bionic pancreas immediately before drinking it. They will be instructed to announce the meal as tiny, small, typical, or large relative to their usual breakfast. They must use the same size meal announcement for each meal challenge they complete on the bionic pancreas.
 - Once they have calibrated their CGM and confirmed the appropriate insulin dose has been delivered by the iLet, subjects will immediately drink the provided 8-ounce BOOST high protein meal replacement drink.
 - Once they finish the BOOST, subjects will be asked to resume fasting for four additional hours,

- until the meal challenge is complete. Water and non-caloric beverages are allowed. Subjects will be instructed to follow the same protocols for treating any hypoglycemia or hyperglycemia that occurs during the fasting period. They will be asked to limit hypoglycemia treatment to simple, rapid-acting carbohydrates over complex carbohydrates wherever possible.
- We will ask subjects to check an additional blood glucose using the provided glucometer 1 hour, 2 hours and 4 hours after drinking the BOOST. Subjects will otherwise be allowed and encouraged to check their blood glucose as needed before, during and after the meal challenge. If they experience prolonged hyperglycemia, study staff may recommend they replace their infusion set. No corrections of insulin or other additional boluses or meal announcements may be taken during the meal challenge.
 - After 4 hours, the meal challenge is complete. At this time subjects are allowed to eat and bolus/announce meals at their discretion.
 - Subjects will document when they did the meal challenges in each arm, including what day and time they drank each BOOST. Insulin doses given, CGM readings and fingerstick blood glucose readings will be collated from the device downloads at the end of each arm for analysis of these meal challenges.

Day 7/Day 1 Visits:

- At the end of the 7-day period, subjects will return to the clinic and answer the post questionnaires for the study arm.
- The body weight of the subject will be documented
- Study staff will review any changes in the participant's medical history or medications to ensure continued eligibility, and any adverse events that may have occurred since their screening visit.

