- All study devices, including the iLet BP and the study glucometer will be downloaded. The memory of the BP will be wiped and it will be re-initialized for the next study period. Diagnostics will be performed to ensure that the Dexcom CGM device is appropriately calibrated and that all of the components of the bionic pancreas are in good communication with each other.
- Used and unused insulin vials will be returned to prevent the subject from using the wrong insulin during the wrong week.
- Anti-insulin antibody and plasma blood samples will be collected.
- Subjects will have the option to begin the next arm of the study on the same day they complete the previous study arm.
 - If subject choose this option, they will start over with Day 1 procedures:
 - If the Dexcom CGM has not already been replaced, it will be replaced at this time.
 - Study staff will provide supplies, including the next week's insulin, and review the study procedures.
 - Study staff will supervise the setup of the iLet and infusion set. Participants will need to fill the iLet with a new reservoir and place a new infusion set at the start of each new study arm.
 - Study staff will start the bionic pancreas and will verify that data streaming is working prior to the subject leaving the Diabetes Research Center.
 - If subjects choose to not continue directly to the next arm of the study, the Dexcom CGM sensor will be removed, all bionic pancreas infusion sites will be removed, subjects will put their own pump back on, and they will be discharged.
 - A provider (MD or NP) will review the last several hours of insulin dosing and assist the subject in resuming their usual care.
 - The next arm of the study will be scheduled to begin up to 14 days from the end of the previous study arm.

Final Day 7 Visit:

- At the end of the 7-day period, subjects will return to the clinic and answer the post questionnaires for the study arm.

- The body weight of the subject will be documented
- Any changes to medications or medical history and any adverse events that may have occurred since the last study visit will be documented
- Anti-insulin antibody and plasma blood samples will be collected
- The Dexcom CGM sensor and all bionic pancreas infusion sites will be removed.
- All study devices, including the iLet BP and the study glucometer will be downloaded.
- Used and unused insulin vials will be returned.

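### The meal challenge is described as using a standardized bolus, but the bolus is learned afresh in each arm and challenge days are not matched across arms, so a participant's arms can be compared at different stages of learning

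*Combined protocol and SAP*

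**What the plan says.** The Meal Challenges part of section V.d.v gives the purpose of the challenges: to help "identify any changes in glucose control on each insulin in response to a standardized meal and bolus". The meal is one 8-ounce drink after about eight hours of fasting. There are two challenges per arm, and they "must be done during days 3-7, but not on the first 2 days of the arm". On the announcement, the rule is: "They must use the same size meal announcement for each meal challenge they complete on the bionic pancreas". On the day, it is: "Subjects will document when they did the meal challenges in each arm, including what day and time they drank each BOOST".

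Other sections describe how the bolus is set:

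- Section V.c (iLet Bionic Pancreas): the size of the meal-priming bolus "will adapt during the course of the trial to meet a target of 75% of the insulin needs for that size and mealtime".
- Section I.b, on the meal-dose controller: "it makes automatic adjustments based on dosing history for similar meal announcements made on previous days".
- Section V.d.v, Day 1 Visits: "The control algorithm will be initialized only with the subject's weight".
- Section V.d.v, Day 7/Day 1 Visits: "The memory of the BP will be wiped and it will be re-initialized for the next study period".

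Section VI.b.2 makes mean postprandial excursion over both challenges a secondary endpoint, and VI.b.3 lists the 4-hour AUC among other outcomes. The planned tests are the paired t-test or the Wilcoxon signed rank test. Section VI.a.2 collects the day, time and insulin doses of each challenge, but the analysis text uses neither day nor dose.

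**The concern.** Holding the announced size constant does not hold the dose constant. The same announcement triggers a dose that depends on what the device has learned from similar announcements earlier in that arm. Nothing requires a participant to do the challenges on the same study days in each arm. One person could do them on days 3 and 4 with one insulin and on days 6 and 7 with another.

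Excursion and 4-hour AUC are the listed outcomes closest to absorption speed, which is the mechanism in the section II hypothesis. If the bolus is called standardized, a difference in excursion may be credited to the insulin's pharmacokinetics when the priming dose also differed. This matters most for individuals. Aim 1 and section VI.b compare arms within a single participant, and with two challenges per arm randomization cannot balance challenge day for one person.

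**Working it through.** The plan gives no sample-size, power or error figure for the meal challenge, so there is nothing of its own to reproduce. The check is a comparison of the sections followed by a count.

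**What is standardized**

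| Element | Fixed across arms? | Source |
|---|---|---|
| Drink and fasting | Yes | V.d.v, Meal Challenges |
| Announced size | Yes | V.d.v, Meal Challenges |
| Starting information | Yes, weight only | V.d.v, Day 1 Visits |
| Challenge days | No, any in 3–7 | V.d.v, Meal Challenges |
| Priming dose | No, adaptive | I.b; V.c |

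**Earlier breakfasts in the arm.** A challenge on day *d* follows *d* − 1 breakfasts if the day-1 breakfast was taken on the device, and *d* − 2 if it came before device start. Day 3 gives 1–2 and day 7 gives 5–6. These are upper limits, because announcing meals is encouraged rather than compulsory and other breakfasts may be announced in another size.

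**Mismatch in days.** Taking the two challenges to be on different days, there are C(5,2) = 10 day pairs per arm. The mean challenge day runs from (3 + 4)/2 = 3.5 to (6 + 7)/2 = 6.5, so two arms can differ by up to 3 days.

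If all pairs were equally likely and chosen independently in each arm (an assumption; the documents say nothing on this), there are 10 × 10 = 100 combinations for two arms:

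| Gap in mean day | 0 | 0.5 | 1 | 1.5 | 2 | 2.5 | 3 |
|---|---|---|---|---|---|---|---|
| Combinations | 16 | 28 | 24 | 16 | 10 | 4 | 2 |

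- Same pair in two arms: 10/100 = 10%; in all three arms: 10/1,000 = 1%.
- Gap of at least 1 day: (24 + 16 + 10 + 4 + 2)/100 = 56%.
- Gap of at least 2 days: (10 + 4 + 2)/100 = 16%.
- Average gap: (14 + 24 + 24 + 20 + 10 + 6)/100 = 0.98 days.
- Range over three arms of at least 1 day: 828 of 1,000 combinations, or 83%.

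**Why no dose figure follows.** Suppose each announcement closes a fraction *r* of the gap between the starting and target bolus, so that (1 − *r*)^*k* of it remains after *k* announcements. Assume *r* = 0.3 to 0.5 and a gap of 4 units; none of these values is in the documents. Take *k* = 2, 3, 5 and 6 on days 3, 4, 6 and 7. The endpoint averages both challenges, so the most extreme contrast is days 3 and 4 against days 6 and 7:

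- *r* = 0.3: 4 × [(0.490 + 0.343)/2 − (0.168 + 0.118)/2] = 1.09 units.
- *r* = 0.5: 4 × [(0.250 + 0.125)/2 − (0.031 + 0.016)/2] = 0.66 units.

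Averaged over the 100 equally likely combinations, the absolute difference is about 0.37 and 0.24 units. If the day-1 breakfast was not announced, *k* falls by one and every difference is divided by (1 − *r*): the extremes become 1.09/0.7 = 1.56 and 0.66/0.5 = 1.3 units. The answer moves with each assumed input, so it illustrates the mechanism and does not estimate the effect.

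**The case against.** Much can be said for the plan. The challenge window, the reset and the weight-only start are the same in every arm, and arm order is randomized. Days 1 and 2 are excluded, two challenges are averaged, and doses are recorded. The stated focus of Aim 1 is which insulin is best in this device, so insulin plus adaptive controller is a legitimate thing to measure. All of this stands, and it limits the point in four ways.

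- A reader might infer that the insulin comparison is biased. The documents do not support that: nothing in them makes the choice of day depend on the insulin. The group-level consequence is noise. They also show only that arms *can* be compared at different stages. That participants choose the days is implied by their recording them, not stated.
- A reader might treat the memory wipe as part of the fault. It is a safeguard: it gives each insulin the same start and stops doses learned on one insulin carrying into the next arm.
- A reader might set one day-3 challenge against one day-7 challenge and, on the assumptions above with *k* = 2 and 6, arrive at 0.9 to 1.5 units. That is not the endpoint, which averages two challenges, and the inputs are assumed. Nor would a priming shortfall pass in full into excursion: the priming bolus is partial, and section V.b allows automated doses up to every five minutes.
- A participant who announces the drink in a size not otherwise used at breakfast has no same-size history at the first challenge in any arm, whatever the day. Matching days does nothing for that participant. Whether sizes share learning is not stated.

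Two things remain. The wording on the bolus conflicts with sections I.b and V.c. And the safeguards leave days 3 to 7 unmatched in a study that compares arms within individuals, where random order gives no protection.

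**Conclusion.** The point holds as a correction of wording and an avoidable source of within-person variation. The bolus is not standardized as the procedures say. A participant's arms can be compared at different stages of bolus learning: at most 1–2 earlier breakfasts against 5–6, with a gap in mean challenge day of up to 3 days. The 56% and 83% figures depend on equally likely day pairs; the maximum gap depends only on the two challenges being on different days.

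For the group comparison this is added noise of unknown size, in a study of up to 30 participants with no formal power analysis. For a single participant it can confound insulin with learning stage. It affects one secondary endpoint and one other outcome, and the co-primary outcomes are not challenge-based. Severity is minor to moderate.

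**What to change.** 1. In section V.d.v, have each participant do the two challenges on the same two study days in all three arms, chosen from days 3–7 before the first arm, and record any deviation. The possible gap in mean challenge day then falls from 0–3 days to 0. Fixed days are already used in the Test Run (days 2 and 3).
2. In the same section, stop describing the bolus as standardized. State that the meal is standardized and that the bolus is adapted by the device. This is needed in any case: matching days aligns only the calendar stage of learning, and the controller will still adapt differently to each insulin.
3. Tabulate by arm the challenge day, the delivered priming dose and the number of earlier same-size breakfast announcements. Section VI.a.2 already collects the data.
4. In section VI.b, interpret excursion and AUC as the effect of the insulin together with the adaptive controller.

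The cost is a few sentences, one descriptive table and slightly less freedom for participants in choosing challenge mornings. No dose or clinical rule changes.
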